2.6.1 Rationale for this Approach

The proposed treatment approach entails radiotherapy to axillary level III and SCV, defined by CT imaging obtained in a prone position using IMRT technique. We anticipate that this will improve target coverage, toxicity, and tolerability for several reasons. First, by avoiding radiotherapy to level I and II axillary lymph nodes in a previously dissected axilla, we anticipate reduced risk of lymphedema. Additionally, treatment in the prone position has been shown to reduce dose to heart and lungs (Formenti, Gidea-Addeo et al. 2007), which may decrease late toxicity to these organs. Finally, while standard 3-field and 4-field techniques provide inadequate lymph node coverage in the prone position (refer to preliminary data in Section 2.6.2), use of IMRT technique will enable prone target coverage while maintaining low doses to normal tissues.

2.6.2 Preliminary Data

To evaluate the dosimetric feasibility of the prone IMRT treatment approach and to compare its dosimetric performance compared to other standard techniques, we explored six treatment planning techniques to target the breast and axillary level III and supraclavicular nodes.

The CT images of 10 breast cancer patients (7 left, 3 right) who underwent simulation in both prone and supine positions were used for planning. Supraclavicular and level III axillary lymph node regions, breast tissue, tumor bed, heart, and ipsilateral lung were manually contoured. Six treatment plans were created for each patient; all utilized tangential fields to target breast tissue. A three-dimensional conformal radiotherapy (3DCRT) plan with a single anterior-oblique field, a 3DCRT plan with anterior-oblique and posterior axillary boost fields, and an intensity-modulated radiotherapy (IMRT) plan were utilized to target regional nodes in both prone and supine positions. Dose-volume histograms were compared to evaluate lymph node coverage and normal tissue dose. Two-tailed student t-test was used to identify statistically significant differences between planning techniques. Nodal target and normal tissue doses from the six techniques are summarized below in Tables 6 - 8.

Table 6 - Prone Compared to Supine Positioning

	mean (st dev, range)	mean (st dev, range)	p-value
	3-field supine	3-field prone	
PTV-V50	53.96% (18.20, 25.70-75.00)	34.10% (21.91, 4.50-73.10)	0.0407559
Lung-V40	14.70% (4.84, 8.30-24.40)	3.81% (4.41, 0.10-14.40)	0.0000530
Lung-V20	22.98% (5.23, 16.50-33.80)	9.52% (5.98, 2.10-21.20)	0.0000434
Lung-V5	31.57% (5.82, 24.00-42.10)	13.57% (6.83, 4.90-27.90)	0.0000056
Heart-V20	0.15% (0.30, 0.00-0.80)	0.04% (0.08, 0.00-0.20)	0.2687512
Heart-V5	0.72% (1.07, 0.00-2.70)	0.38% (0.44, 0.00-1.20)	0.3436903
Spinal cord- Dmax	1131.90 cGy (333.38, 782.00-1712.00)	889.60 cGy (273.04, 263.00-1258.00)	0.0922816
	IMRT supine	IMRT prone	
PTV-V50	94.59% (0.32, 94.00-95.00)	95.48% (0.69, 94.80-97.00)	0.0016879
Lung-V40	15.28% (3.06, 11.90-21.80)	6.54% (1.98, 3.50-9.00)	0.0000005
Lung-V20	27.22% (6.88, 18.60-37.80)	12.48% (3.29, 8.20-17.90)	0.0000089
Lung-V5	43.73% (7.47, 32.30-56.90)	24.18% (5.09, 19.50-33.40)	0.0000021
Heart-V20	0.12% (0.26, 0.00-0.70)	0.37 (0.72, 0.00-2.00)	0.3011538
Heart-V5	0.62% (0.93, 0.00-2.40)	0.93% (1.08, 0.00-3.70)	0.6524424
Spinal cord- Dmax	3490.70 cGy (765.64, 1963.00-4266.00)	2805.20 cGy (953.84, 1762.00-4112.00)	0.0932683
	4-field supine	4-field prone	
PTV-V50	60.77% (12.56, 36.90-83.50)	38.93% (20.65, 1.80-78.60)	0.0104802
Lung-V40	12.29% (7.38, 0.70-25.30)	5.59% (4.70, 0.00-15.60)	0.0262689
Lung-V20	20.53% (8.34, 2.20-34.10)	10.93% (6.65, 2.10-26.30)	0.0107219
Lung-V5	29.78% (10.27, 5.60-43.70)	16.40% (8.19, 5.90-36.50)	0.0047406
Heart-V20	0.50% (1.05, 0.00-2.80)	0.06% (0.10, 0.00-0.20)	0.2870816
Heart-V5	1.84% (3.09, 0.10-8.50)	0.53% (0.42, 0.20-1.20)	0.2864321
Spinal cord- Dmax	836.20 cGy (225.60, 560.00-1258.00)	739.10 cGy (134.95, 418.00-872.00)	0.2580200

These results indicate that all 3DCRT plans had inadequate lymph node coverage, with mean planning target volume (PTV) V50 Gy 54% supine and 34% prone (3-field 3DCRT), and 61% supine and 39% prone (4-field 3DCRT). Compared to these techniques, IMRT significantly improved nodal coverage, with mean PTV V50 Gy 95% supine and 95% prone ($p < 0.001$, two-tailed t-test). Protocol Type / Version # / Version Date Version 5.4 06/30/2017

tailed t-test). Prone positioning resulted in significantly lower ipsilateral lung doses: mean V20 Gy was 10% prone versus 23% supine (3-field 3DCRT, $p < 0.001$, two-tailed t-test); 21% supine versus 11% prone (4-field 3DCRT, $p = 0.01$, two-tailed t-test); and 12% prone versus 27% supine (IMRT, $p < 0.001$, two-tailed t-test). Among the 7 left breast

Table 7 - Supine IMRT Compared to Supine 3F/4F

	mean	mean	p-value
	3-field supine	IMRT supine	
PTV-V50	53.96	94.59	0.0000014
Lung-V40	14.70	15.28	0.7525528
Lung-V20	22.98	27.22	0.1382071
Lung-V5	31.57	43.73	0.0007318
Heart-V20	0.15	0.12	0.8059355
Heart-V5	0.72	0.62	0.8108750
Spinal cord-Dmax	1131.90	3490.7	0.00000005
	4-field supine	IMRT supine	
PTV-V50	60.77	94.59	0.0000001
Lung-V40	12.29	15.28	0.2521097
Lung-V20	20.53	27.22	0.0027134
Lung-V5	29.78	43.73	0.0027134
Heart-V20	0.5	0.12	0.4401863
Heart-V5	1.84	0.62	0.4509997
Spinal cord-Dmax	836.2	3490.7	0.00000004

Table 8 - Prone IMRT Compared to Prone 3F/4F

	Mean	mean	p-value
	3-field prone	IMRT prone	
PTV-V50	34.10	95.48	0.0000001
Lung-V40	3.81	6.54	0.0909352
Lung-V20	9.52	12.48	0.1876868
Lung-V5	13.57	24.18	0.0009626
Hrt-V20	0.04	0.37	0.1577367
Hrt-V5	0.38	0.93	0.2202274
Cord-Dmax	889.60	2805.20	0.0000091
	4-field prone	IMRT prone	
PTV-V50	38.93	95.48	0.0000001
Lung-V40	5.59	6.54	0.5635124
Lung-V20	10.93	12.48	0.5172072
Lung-V5	16.4	24.18	0.020405
Hrt-V20	0.06	0.37	0.2744447
Hrt-V5	0.53	0.93	0.2089303
Cord-Dmax	739.1	2805.20	0.0000024

cancer patients, there was no statistically significant difference in mean heart V20 Gy or V5 Gy ($p > 0.05$, two-tailed t test).

2.7 Quality of Life Assessment

Quality of life (QOL) assessments will be performed by patients at regular intervals (i.e., baseline, last week of treatment, 45 - 60 days from starting radiotherapy and 2-year follow-up). Patients status post mastectomy will be asked to answer applicable questions only in the QOL assessment. This trial will use the QLB and QLF questionnaires from the RTOG.

The QLB and QLF questionnaires are derived from a validated integration of parts of the BCTOS and MOS SF 36. BCTOS is a validated questionnaire that measures cosmetic results based on patient self-reports. This brief self-report instrument has high reliability and validity, and has been used in a variety of previous studies on recovery from breast cancer treatment (Stanton, Krishnan et al. 2001). MOS SF36 is a common QOL questionnaire used in cancer patients (Shelbourne 1992; Ware and Sherbourne 1992).

2.8 Measuring the Late Toxicities of Breast and Nodal Radiation

Hoeller et al. recently reported a careful comparison of The Radiation Therapy Oncology Group (RTOG) and Late Effects Normal Tissue Task Force subjective, objective, management, and analytic (LENT/SOMA) scores for late breast toxicity after radiation in a group of breast cancer patients (Hoeller, Tribius et al. 2003). In comparison, when LENT/SOMA criteria were used, telangiectasia and pigmentation were upgraded in 34% and 36% of patients, respectively, and

telangiectasia was downgraded in 45% of patients. Inter-observer variability was similar for both classification systems and ranged from Cohen's kappa 0.3 (retraction) to 0.91 (telangiectasia). The authors concluded that LENT/SOMA criteria seem to be the better tool in grading and recording late radiation toxicity as compared to the RTOG scale. Specifically, fibrosis scores correlated well with the LENT/SOMA scoring system (Spearman's rho 0.78, p = 0.01). The LENT/SOMA scoring system will be used in the reporting of late radiation morbidity in this protocol.

2.8.1 Quantitative Measurement of Thyroid Function

Patients undergoing radiotherapy for invasive breast cancer are at higher risk of hypothyroidism. One recent study documented hypothyroidism in 18% of patients with stage II/III invasive breast cancer who had undergone radiotherapy, compared to only 6% (p < 0.001) of an age-matched control group from the general population (Reinertsen, Cvancarova et al. 2009).

As such, patients will undergo thyroid function testing, including measurement of serum thyroid stimulating hormone (TSH) and free T₄ levels, at baseline and at yearly intervals after completion of radiotherapy.

2.8.2 Quantitative Measurement of Lymphedema

Patients will be assessed for lymphedema at baseline, end of treatment, and at yearly intervals after completion of radiotherapy. Arm circumference at sites 10 cm above and below the antecubital fossa will be obtained. Mild, moderate, and severe lymphedema is defined as a difference of 0.5 to 2 cm, 2.1 to 3 cm, and greater than 3 cm, respectively, of arm circumference at one or more measurement sites on the treated versus untreated side. Lymphedema progression is defined as transition from lower to higher grade at any time point. Similar lymphedema classification systems have been used in previously published studies (Keramopoulos, Tsionou et al. 1993; Bar Ad, Cheville et al. 2009).

2.8.4 Genetics of Radiation-induced breast fibrosis

Since the most likely long-term toxicity of accelerated radiation is soft tissue fibrosis and skin telangiectasia the preliminary recognition of genetic predispositions to these complications enables the exclusion of high-risk carriers from the trials of accelerated/hypo-fractionated radiation. In other words, similar to the impact of pharmacogenomics in medical oncology, the field of radiation-genomics is also rapidly emerging, permitting identification of individuals with genetic predisposition to inferior repair of the damage caused by ionizing radiation.

A recent study from Quarmby et al. has shed some light on the genetic risk of developing breast fibrosis post-ionizing radiation. To investigate whether single nucleotide polymorphisms (SNP) of transforming growth factor beta-1 (TGF-beta1) were associated with the susceptibility of

breast cancer patients to severe radiation-induced normal tissue damage, Quarmby et al. performed Polymerase Chain Reaction-Restriction Fragment Length Polymorphism (PCR-RFLP) assays for TGF-beta1 gene polymorphisms on DNA obtained from 103 breast cancer patients who received radiotherapy (Quarmby, Fakhoury et al. 2003). The G-800A, C-509T, T+869C and G+915C polymorphic sites were examined, and genotype and allele frequencies of two subgroups of patients were calculated and compared. The investigators found that the less prevalent -509T and +869C alleles were significantly associated with a subgroup of patients who developed severe radiation-induced normal tissue fibrosis (n = 15) when compared with those who did not (n = 88) (odds ratio = 3.4, p = 0.0036, and 2.37, p = 0.035, respectively). Furthermore, patients with the -509TT or +869CC genotypes were between seven and 15 times more likely to develop severe fibrosis. These findings imply a role for the -509T and +869C alleles in the biological mechanisms underlying susceptibility to radiation-induced fibrosis.

2.8.5 Blood Collection for Future Genomic Studies

The purpose of this portion of the study will be to collect blood from each subject accrued to the study for the -509C→T and +869T→C TGF-β1 polymorphisms that have been reported to be correlated with the development of fibrosis following radiotherapy for treatment of breast cancer (Quarmby, Fakhoury et al. 2003).

It is first important to note that [name] (co-investigator) laboratory has extensive experience in the detection of genetic alterations using Denaturing High Performance Liquid Chromatography (DHPLC) (Atencio, Iannuzzi et al. 2001; Iannuzzi, Atencio et al. 2002; Bernstein, Teraoka et al. 2003). In addition, our group is part of the WECARE consortium of four laboratories that is in the process of using DHPLC to screen 2100 breast cancer patients for mutations and SNPs in a variety of genes associated with DNA repair and radiation responses. Hence, our laboratory has substantial expertise performing genetic analysis using DHPLC and will therefore be able to immediately implement this portion of the project.

For the purpose of this trial blood will be collected to enable future genomic analysis for this polymorphism to explore association with the incidence of grade 3 and 4 late complications at 3 years follow up and for other related research studies. Methods details of DHPLC are covered in Section 10.4.

3 PATIENT SELECTION

For Cohort A : Include patients who have undergone SLNB without completion ALND)

3.1 Inclusion Criteria

3.1.1 Pre- or post-menopausal women with stage II - III breast cancer (AJCC 2002)

3.1.2 Biopsy-proven invasive breast cancer, excised with negative margins of at

- least 1 mm
- 3.1.3 Status post segmental mastectomy or mastectomy and axillary node dissection with removal of at least 8 nodes
- 3.1.4 One to 5 involved lymph nodes identified at axillary staging
- 3.1.5 At least 2 weeks from last chemotherapy or before chemotherapy
- 3.1.6 No more than sixty days from final surgery to simulation if no systemic therapy (includes chemotherapy and Hormonal therapy) is given
- 3.1.7 Patient needs to be able to understand and demonstrate willingness to sign a written informed consent document

3.2 Exclusion Criteria

- 3.2.1 Previous radiation therapy to the ipsilateral breast
- 3.2.2 More than 5 involved nodes identified at axillary staging
- 3.2.3 Current treatment for active connective tissue disorders, such as lupus or scleroderma
- 3.2.4 Pregnant or lactating women
- 3.2.5 Less than 35 years old
- 3.2.6 Prior concurrent malignant other than basal or squamous cell carcinoma or carcinoma in situ of cervix unless disease free > 3years

4 REGISTRATION PROCEDURES

4.1 General Guidelines

Patients will have completed all breast surgical procedures prior to accrual into this protocol in order to establish eligibility criteria. Final pathology margins must be at least 1 mm in all directions to be eligible. The patient may undergo re-excision if the initial margins are involved or close (< 1 mm). If the patient meets the eligibility criteria after re-excision, she may be entered into the left or right breast cancer strata. AJCC staging criteria will be used to identify clinical stage II - III breast cancer patients' eligible to this study. All eligible women who are referred to the Radiation Oncology Department at NYU School of Medicine for radiation following surgery for breast cancer will be offered the opportunity to participate in this experimental protocol.

4.2 Registration Process

Before any protocol specific procedures can be carried out, investigators/staff will fully explain the details of the protocol, the study procedures and the aspects of patient privacy regarding research information. Patients or their legal guardians will be provided a comprehensive explanation of the proposed treatment including the type of therapy, the rationale for treatment on the protocol, alternative treatments that are available, any known adverse events, the investigational nature of the study and the potential risks and benefits of the treatment. The informed consent document will meet all requirements of the Institutional Review Board (IRB). All subjects/patients are informed in the consent that participation or refusal to participate in the

research study will not affect any of the clinical treatment or services to which they would otherwise be entitled.

The physicians who may obtain informed consent are listed on the title page of this protocol. The informed consent form will be signed by the participant and the registering physician. Once signed, a copy will be given to the patient and one will be maintained with the patient's medical record. Once eligibility is confirmed and informed consent is documented, the patient will be registered by the study coordinator/data manager.

5 TREATMENT PLAN

5.1 General Concomitant Medication and Supportive Care Guidelines

During radiation treatment, all patients will be prescribed daily application of Calendula lotion or equivalent, to prevent skin dryness and reduce erythema.

5.2 Duration of Therapy

The treatment will consist of 15 fractions, with one fraction daily for five days a week, for 3 consecutive weeks.

5.3 Duration of Follow-up

Patients will be seen for follow-up at 45 - 60 days from first radiotherapy treatment, and then yearly for up to 5 years.

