2.2 NYU Experience on Accelerated Concomitant Boost Whole Breast: NYU 03-30

Inspired by the hypo-fractionated Canadian trial (Whelan, MacKenzie et al. 2002) we developed a technique that utilizes IMRT to deliver accelerated prone whole breast radiotherapy with a concomitant boost to the tumor bed. The rationale for adding a boost to the tumor cavity derived from the results of a prospective randomized trial conducted by the EORTC (Bartelink, Horiot et al. 2001). A recent update of the trial demonstrated a 10-year cumulative incidence of local recurrence of 10.2% versus 6.2% for the no boost and the boost group respectively ($p < 0.0001$) (Bartelink, Horiot et al. 2007).

Patients with stage I or II breast cancer, excised by breast conserving surgery with negative margins, and either sentinel node biopsy or axillary dissection were eligible for study NYU 03-30. CT simulation was performed with the patient on a dedicated prone breast board, in the exact position used for treatment.

From September 2003 to August 2004, the planned accrual was completed, with 90 patients treated in the protocol (mean follow-up of 39 months, range 1 - 72 months). Median age was 58 years old (range 28 – 80 yo). Median tumor size was 13 mm (range 1 - 40 mm). Acute toxicity was generally mild and is summarized in Table 1 (RTOG score). Most common toxicity was radiation dermatitis, which tended to occur the week after completion of treatment.

Table 1 - Acute Toxicity Observed from Study NYU 03-30

	Grade 1	Grade 2	Grade 3	Grade 4
Dermatitis	38 (42%)	9 (10%)	2 (2%)	-
Fatigue	15 (17%)	-	-	-
Breast edema	7 (8%)	-	-	-
Breast pain	4 (4%)	-	-	-

Longer follow up is required to assess local control, late toxicity, and to determine cosmetic results. Because of blood collection, once sufficient time has elapsed to measure late effects, the study will enable us to explore associations between specific genomic profiles and the

occurrence of fibrosis (Formenti 2005). In addition, this trial generated preliminary data on dose sparing to the heart and lung when patients are treated prone (Darby, McGale et al. 2005).

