9 ADVERSE EVENTS: LIST AND REPORTING REQUIREMENTS

9.1 Adverse Events and Potential Risks List

Expected toxicities include fatigue and skin reactions within the radiation field. Erythema, dry and moist desquamation of the skin will be recorded weekly. Breast edema and tenderness are additional possible acute side effects. Acute (\leq 60 days after first day of treatment) and late toxicity ($>$ 60 days after first day of treatment) will be reported as scheduled in the study calendar. This study will utilize the descriptions and grading scales as described in *Common Terminology Criteria for Adverse Events v3.0 (CTCAE)* for acute toxicity and in the LENT/SOMA classification for late toxicities (appendix 1). Toxicities will be tracked using the Toxicity Tracking Form (appendix 2).

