12 STUDY CALENDAR

Study Procedure	Pre Treatment	Weekly	Last week	Post Treatment (day 45 - 60)	Post Treatment (once/year)
History & Physical	X				
Mammogram and/or breast MRI ^a	X				X ^b
Lumpectomy pathology report	X				
BREAST-focused exam, KPS	X	X		X	X
Lymphedema assessment	X		X		X
Blood for TGF-BETA Polymorphisms and other related research studies	X		X ^c		
Quality of Life Questionnaires ^d	X		X	X	X
LENT/SOMA assessment ^e					X
Thyroid Testing (TSH, T4)	X				X

- a. Standard mammogram or MRI for both breasts.
- b. At each follow-up visit beginning 1 year after completion of radiation treatment a non invasive measurement of fibrosis in the treated breast will be performed using clinical breast exam.
- c. Last day of treatment, after last dose of radiation
- d. QOL will be assessed using the RTOG validated self-assessment questionnaires QLB & QLF (see Appendix 3) at baseline, week 3, day 45 - 60 and 2-yr follow-ups.
- e. Patients will be seen after completion of treatment at day 45 - 60 and then yearly for 5 years total follow up to assess long term sequelae by LENT/SOMA scale.

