14.3.1 Primary Endpoints

The primary outcome of this study is the proportion of patients with acute toxicity greater than grade 2 (Skin toxicities grade 3 and above) occurring within 60 days after first day of treatment. This rate will be estimated with an exact 95% confidence interval. Treatment feasibility will be evaluated for each patient by the ability to meet all physics dose constraints as outlined in section 7.5.6. The proportion of patients who meet the constraints will be estimated with an exact 95% confidence interval.

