APPENDIX 2 – TOXICITY TRACKING FORM

Department of Radiation Oncology
NYU Hospitals Center
[name]
New York, NY 10016

PHYSICIAN'S PROGRESS NOTE

Fraction: 1-5 6-10 11-15 45-60 day F/U

The following critical elements of the patient's weekly exam have been covered:

- Chart & Dosimetry, Treatment set up & positioning review*
- Port Film or image review*
- Examination of patient for evaluation and progress of treatment (see notes below)*

Progress note: _____

Please indicate Toxicity due to Radiation Treatment on the following chart:

	Grade 0	Grade 1	Grade 2	Grade 3	Grade 4
FATIGUE					
	No change	Mild fatigue over baseline	Moderate or causing difficulty performing some ADL	Severe fatigue interfering with ADL	Disabling
RADIATION DERMATITIS					
	No change	Faint erythema or dry desquamation	Moderate to brisk erythema; patchy moist desquamation, mostly confined to skin folds and creases; moderate edema	Moist desquamation other than skin folds and creases; bleeding induced by minor trauma or abrasion	Skin necrosis or ulceration of full thickness dermis; spontaneous bleeding from involved site
PAIN (Breast)					
	No pain	Mild pain not interfering with function	Moderate pain; pain or analgesics interfering with function, but not interfering with ADL	Severe pain; pain or analgesics severely interfering with ADL	Disabling

Attending Signature: _____ Date: _____

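### No skin grading is scheduled from the last treatment week to day 45-60, and the form never asks for the worst grade in between, so the 60-day grade 3+ skin rate can be under-counted by an unknown amount.

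*Combined protocol and SAP*

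**What the plan says.** Section 14.3.1 defines the primary outcome as the proportion of patients with skin toxicity of grade 3 or above "occurring within 60 days after first day of treatment". Of the analysis it says "This rate will be estimated with an exact 95% confidence interval". Section 14.5 adds that a rate above 5% is unacceptable, and Table 9 gives stopping boundaries at 52 and 104 patients.

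The assessment schedule is set in four places:

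- Section 5.3: "Patients will be seen for follow-up at 45 - 60 days from first radiotherapy treatment, and then yearly for up to 5 years".
- Section 12 (study calendar): the row "BREAST-focused exam, KPS" is marked before treatment, weekly, at day 45-60 and yearly. The calendar has no column between the last treatment week and day 45-60.
- Section 9.1: "Erythema, dry and moist desquamation of the skin will be recorded weekly". No end is stated, but the same section refers toxicity reporting to the calendar.
- Appendix 2: the form's time points are "Fraction: 1-5 6-10 11-15 45-60 day F/U". Its instruction is "Please indicate Toxicity due to Radiation Treatment on the following chart". It has no look-back period, worst-grade item or onset date.

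On timing, Section 2.2 reports from the earlier in-house trial (NYU 03-30): "Most common toxicity was radiation dermatitis, which tended to occur the week after completion of treatment".

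**The concern.** The endpoint covers every day up to day 60, but skin is examined on schedule only up to the third treatment week and then once at day 45-60. The unobserved stretch begins with the week in which the protocol's own experience says dermatitis tends to occur.

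A grade 3 reaction that is present at the last weekly score, or still present at the visit, is captured. One that starts after the last weekly score and heals before the visit depends on the patient mentioning it and the clinician choosing to score it. Two clinicians can read the form differently, one scoring the skin as it looks that day and the other the worst since the last visit. The same history would then give different endpoint values.

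A missed event can only lower the observed rate and its confidence interval, so the bias favours calling the regimen acceptable.

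**Working it through.** **1. Length of the gap.** Inputs: 15 fractions, one per weekday (5.2), and the next visit at day 45-60 (5.3). Counting the first fraction as day 1, the last falls on day 19 with a Monday start and on day 21 with any other start, assuming no breaks.

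- Shortest gap: 45 − 21 = 24 days.
- Longest gap: 60 − 19 = 41 days.
- With a Monday start, the week after treatment is days 20 to 26, wholly inside the gap.

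**2. What Section 2.2 supports.** Its Table 1 lists 38 grade 1, 9 grade 2 and 2 grade 3 dermatitis cases among 90 patients, so 38 + 9 + 2 = 49 of any grade. The remark on timing covers all grades. When the two grade 3 cases began and healed is not given.

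**3. Other routes by which an event could be recorded.**

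| Route | Scheduled CTCAE grade in the gap? |
|---|---|
| Weekly recording (9.1) | No; the form's weekly boxes stop at fractions 11-15 |
| Event report forms (9.3) | No; they have no time points |
| QLF questionnaire at day 45-60 (Appendix 3) | No; patient-rated bother over four weeks |

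Taking four weeks as the 28 days before completion and a Monday start, the QLF covers all of days 20-26 if completed on days 45-48, part of them on days 49-54, and none on days 55-60. On day 55, for example, it reaches back only to day 27.

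**4. The plan's own decision lines, as counts.**

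- Interim: 0.1153 × 52 = 5.996, so 6/52 crosses and 5/52 does not.
- Final: 0.097 × 104 = 10.09, so 11/104 crosses and 10/104 does not.
- The 5% statement in 14.5: 6/104 = 5.8% is above it, 5/104 = 4.8% is not.

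**5. Effect of one missed event on the estimate.** The proportion falls by 1/104 = 0.96 points. The exact (Clopper-Pearson) limits for x events in n are the 2.5% quantile of Beta(x, n − x + 1) and the 97.5% quantile of Beta(x + 1, n − x).

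| Count | Rate | Exact 95% CI |
|---|---|---|
| 2/104 | 1.9% | 0.2% to 6.8% |
| 1/104 | 1.0% | 0.02% to 5.2% |
| 6/104 | 5.8% | 2.1% to 12.1% |
| 5/104 | 4.8% | 1.6% to 10.9% |
| 11/104 | 10.6% | 5.4% to 18.1% |
| 10/104 | 9.6% | 4.7% to 17.0% |

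The upper limit drops by 1.53 points (2 to 1), 1.27 points (6 to 5) and 1.17 points (11 to 10). Between 11 and 10 events the lower limit also passes from above 5% to below it.

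**6. Effect on the Table 9 decision (illustration only).** The documents give no missed share, so shares s of 0, 10% and 25% are assumed, each event being missed independently with probability s. With X1 and X2 independent Binomial(52, p(1 − s)), the chance of crossing is P(X1 ≥ 6) + Σ P(X1 = x) · P(X2 ≥ 11 − x), summed over x = 0 to 5.

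| True rate p | s = 0 | s = 10% | s = 25% |
|---|---|---|---|
| 2.2% (2/90 in NYU 03-30) | 0.10% | 0.06% | 0.02% |
| 7.8% (upper exact 95% limit for 2/90) | 29% | 20% | 10% |
| 10% (the plan's alternative) | 57% | 44% | 25% |

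The 57% with nothing missed is below the 80% power stated in 14.5. That is a separate matter and is not caused by the gap.

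**The case against.** The strongest reply is that nothing in the plan excludes these events. The endpoint wording is already cumulative, the form asks about toxicity due to treatment rather than that day's skin, and it has a free-text note, so an investigator who knows 14.3.1 would enter a reaction from day 24. Event forms are required for all adverse events with no end date. The QLF asks about blistered or moist, raw skin and, with a Monday start, reaches at least part of the week after treatment on 10 of the 16 permitted days.

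The evidence is also thin. In the earlier trial 47 of the 49 dermatitis cases were below grade 3. It used RTOG scoring and whole-breast treatment, and nothing shows that a grade 3 reaction would start and heal inside the gap. At 2/90 the effect on the stopping decision is negligible; larger effects need a true rate about 3.5 to 4.5 times as high (7.8/2.2 and 10/2.2). Finally, grading from recall can confuse grades 2 and 3 in either direction.

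Most of this stands, and it limits the claim to a possible under-count of unknown size. It does not remove it. None of these routes yields a scheduled CTCAE grade in the gap, and a form completed as printed can leave out a healed grade 3 reaction. Recall error is a real cost, which is why the examined-only rate belongs beside the fuller one.

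**Conclusion.** The concern holds. No skin grade is scheduled for 24 to 41 days of a 60-day endpoint window, assuming no treatment breaks. That interval contains the week when dermatitis tended to occur in the sponsor's earlier trial, and the form has no prompt to look back.

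The primary rate can therefore be too low by an amount the documents do not allow one to calculate. The per-event effect on the estimate and interval needs no assumption about the missed share. The effect on stopping rests on assumed shares and matters only if the true rate is well above 2/90. The change should be made because it is cheap and protects the primary estimate. Confidence is medium because the timing and healing of grade 3 reactions are not documented.

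**What to change.** In Appendix 2, at day 45-60, keep the current grade and add one field: the worst CTCAE skin grade since the fractions 11-15 score, with its date, taken from the patient's report and any clinic or telephone records. Print the full grade 3 and grade 4 radiation dermatitis definitions from Appendix 1 beside it.

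In 14.3.1, define the endpoint as the maximum grade over the weekly scores, the day 45-60 score, the new worst-grade score and any unscheduled contact. Also report the rate from directly examined grades alone, so the reader can see how much rests on recall.

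The cost is one form field and an amended endpoint definition, with no added visit. The drawbacks are recall over as much as 41 days from the last fraction (60 − 15 = 45 days if the last weekly score was at fraction 11, day 15 with a Monday start), possible error between grades 2 and 3 in either direction, and perhaps a slightly less favourable observed rate.
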